The study is a sub-study of the PROTON project, which is sponsored by a grant of 60 mio. DKK from the Novo Nordisk Foundation Grant number: NNF14OC0013659 and is expected to cover all costs related to the project. The budget assigned for the study covers 1.265.653 DKK. The grant-money is held on a research account administered by Steno Diabetes Center Copenhagen. No financial compensation will be given for patients participating in the study. Healthy controls will be offered 500 DKK (taxable) for participation in the study. Documented transportation expenses for all participants will be covered after the lowest applicable rate in Region Hovedstaden. The investigators have no financial conflict of interest in relation to the procedures or investigations in the study.

Ethical considerations:

Dapagliflozin is approved for the treatment of type 1 diabetes and type 2 diabetes and clinical trials have shown beneficial effects of dapagliflozin treatment on glycaemic control, weight and blood pressure. In addition, cardiovascular outcome trials have shown long-term cardioprotective and renoprotective effects. As this is a single-dose study, these benefits are not expected to occur in the participants.

Study participants will have the benefit of the individual results from kidney scans, blood tests and the autonomic function assessment, which are not necessarily carried out routinely at Steno Diabetes Center Copenhagen. Individual results will be given by the project responsible doctor. The participants' right not to know their own data will be respected.

Regardless of the outcome, the results and knowledge obtained from the project is believed to contribute to a better understanding of the mechanisms behind development and progression of diabetic nephropathy and thereby, in general, contribute to a possible improved treatment of diabetic kidney disease in the long term. This will benefit all patients with diabetes worldwide. In the opinion of the investigators it can be concluded that potential discomforts and risks are compensated by the expectable advantages of conducting this study.

The study may be stopped by the investigator if new information appears about the medicine that causes safety problems. Subjects will be informed accordingly.

Patient risks and management of complications

The risk is considered very small with treatment with two single doses of 50 mg, even if these doses are larger than usually applied daily doses (10 mg per day), as side effects have not been observed with this or higher doses (up to 500 mg as single dose). After longer periods of using dapagliflozin, the following side-effects have been observed: Hypoglycemia, hypotension, elevated hematocrite, dyslipidemia, back pain, dizziness, skin rash, urinary tract infection, vulvovaginitis and dehydration. Very rare incidents of ketoacidosis have been observed. If the mentioned side-effects against all expectations should occur, it is common for them, that they are transient or simple to manage with standard treatment methods. Blood sampling by arterial puncture and venous puncture can cause a short pain, a small risk of hematoma and a minimal infection risk at the puncture site. Arterial puncture is also

associated with a minimal risk of arteriospasm, nerve damage, fainting and thrombosis (25). The most feared complication is irreversible ischemic damage distally for the thrombosis-site. This will only happen if revascularization is not achieved before six hours after the vascular occlusion. Due to access to nearby vascular surgery, irreversible ischemic damage is not considered a realistic ultimate consequence of potentially occurring thromboses during the present study. Usually there is no discomfort associated with MRI scans. Short-term transient side-effects can be experienced: Slight increase in body temperature (< 0.6 °C), touch sensations, dizziness, nausea and taste of metal. Besides this, it can feel claustrophobic to lie in the scanner.

Complications that might occur will be managed and followed up relevantly by the investigators.

Participant information/informed consent

The participants are informed that participation in this research project is entirely voluntary. For all participants, the oral information is given at the information meeting by the investigator in calm surroundings. These surroundings are secured by having the meeting in a suited room with the possibility of closing the door. The participant is entitled to ask questions and bring a friend or relative to the information meeting, as described in the written information. Before informed consent is signed, the participant will be given the opportunity for at least 24 hours for consideration. In case the participant, after having been asked, does not express a need for further time for reflection, the informed consent is obtained at the information meeting. The participants will be informed that they at all times and without justification may withdraw their informed consent and choose no longer to participate in the study without any implications for their future treatment at Steno Diabetes Center Copenhagen. After signed informed consent, the study investigators, the regional ethical committee and other relevant authorities will have the possibility of accessing the medical records of the study participants in order to verify and monitor the project procedures and project data, provided confidentiality is kept. The participants are given a copy of the signed consent. Information on individual data and interpretation hereof will be communicated by the study dedicated doctor. The participant's right not to know their own data will be

respected. No study-specific tests are performed before informed consent for the study is obtained.

Publication plan

The study is initiated by [name]. Data is owned by the investigators. Positive, inconclusive as well as negative study results will be published in both national and international oral and written presentations as well as peer-reviewed international scientific journals. If data against expectations are not published in international journals, positive as well as negative study results will be published on a public website, for example www.clinicaltrials.gov.

Timeframe

Protocol finished	November 2019
Scientific Ethical Committee approval	December 2019
Inclusion of patients from	January 2020
Study completed (last participant, last visit)	January 2021
Data analysis (primary endpoint)	Spring 2021
Presentations	Autumn 2021
Publications	Winter 2021

References

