The sodium-glucose cotransporter-2 (SGLT2) is selectively expressed in the human kidney, where it executes reabsorption of filtered glucose with a high capacity. As a therapeutic target, SGLT2 has been successfully engaged by orally active, selective agents. SGLT2 inhibition (SGLT2i) has a range of known physiological effects: Glycosuria, natriuresis, plasma volume reduction, blood pressure reduction, increased lipid oxidation and ketogenesis (2). However, only few studies have described renal physiologic effects of SGLT2 inhibition in humans, where it has been observed that hyperfiltration and renal plasma flow is reduced during clamped euglycemia in type 1 diabetes (3).

SGLT2i have been observed to reduce cardiovascular mortality and to be associated with slower progression of diabetic kidney disease in the EMPA-REG-trial (4, 5); to reduce risk of cardiovascular events and kidney failure in the CREDENCE-trial (6); to slow progression of albuminuria in the CANVAS-trial (7); and to reduce the risk of renal events in the DECLARE-trial (8). The SGLT2 inhibitor dapagliflozin, used in the DECLARE study, reach peak plasma concentration after two hours and based on glucose excretion, the renal effects seem to be present after a few hours. The half-life is approximately 17 hours (9). The exact mechanisms of the beneficial effects of SGLT2 inhibition in diabetes is still unknown, but several hypotheses have been suggested. Hypoxia might play an important role.

Renal hypoxia

The kidneys have a high oxygen consumption, needed for reabsorption of filtered solutes, mainly sodium. While the renal cortex has a high perfusion, the renal medulla has a low

perfusion and at the same time a high oxygen demand needed for sodium reabsorption in the ascending loop of Henle, making it more prone to hypoxia. The presence of hypoxia has been demonstrated in diabetic kidney disease compared to age-matched healthy controls (10). At the same time, there is strong evidence of tissue hypoxia playing a central pathogenic role in the development of chronic diabetic kidney disease (11, 12). This is supported by a recent study showing that renal cortical hypoxia predicts decline in renal function in subjects with chronic kidney disease (13).

In diabetes, a number of factors can act together and increase the risk of renal hypoxia (14):

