We hypothesize that SGLT2 inhibition acutely reduces the kidneys demand for oxygen by reducing renal metabolism due to blocked sodium-glucose transportation, and hyperfiltration. We hypothesize that the following changes can be demonstrated after institution of SGLT2 inhibition:

- 1) Lowering of renal artery flow (PC-MRI)
- 2) Lowering of renal cortical perfusion and the ratio of cortical/medullary perfusion (ASL-MRI)
- 3) Better medullary oxygenation: Lowering of the renal medulla T_2^* (BOLD-MRI)
- 4) Decrease of renal oxygen consumption (Q-flow combined with measurement of BOLD in renal artery and vein)

We further hypothesize that autonomic function will improve, and that peripheral blood oxygenation and mitochondrial function will both increase after institution of SGLT2 inhibition.

Study population

Fifteen healthy controls recruited through an advertisement in the local newspapers and 15 persons with type 1 diabetes recruited from Steno Diabetes Center Copenhagen according to the study in-and exclusion criteria.

Inclusion criteria healthy controls:

- Written informed consent must be provided before participation
- Male or female patients > 18 years of age
- Capable of lying in a MR-scanner for two hours

Inclusion criteria persons with type 1 diabetes:

- Written informed consent must be provided before participation
- Male or female patients >18 years of age with a diagnosis of type 1 diabetes (WHO criteria)
- Urinary albumin creatinine ratio (UACR) ≥ 30 mg/g in 2 out of 3 consecutive samples (albuminuria) prior to randomization assessed from electronic laboratory database.
- Capable of lying in a MR-scanner for two hours

Exclusion criteria for all:

- Non-diabetic kidney disease as indicated by medical history and/or laboratory findings
- Renal failure (eGFR<15 ml/min/1.73m²), dialysis or kidney transplantation
- Treatment with beta-blocking medication
- Uncontrolled arrhythmia, 2. or 3. degree AV-block or sick sinus syndrome - assessed from a standard 12-lead electrocardiogram
- Pregnancy or breastfeeding (urine HCG is performed on all fertile women)
- Systolic blood pressure < 90 or > 200 mmHg
- Patients who, in the judgement of the investigator, is incapable of participating
- Exclusion criteria for MRI
 - Claustrophobia
 - Known heart disease

- Known lung disease
- Have had surgery the past six weeks
- Have foreign bodies of metal in the body (e.g. pacemaker, metal plates, metal screws)

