Information about the study background, design and aspects of the study will be given by the investigator. After consideration, the participants interested in participating in the study are asked to sign an informed consent form. After signed informed consent, patients will be randomized. See section "Participant information/informed consent" for details on informed consent.

Visit 1 (day 7±6) at Steno Diabetes Center Copenhagen

The study participant will come fasting from the morning and abstinent from medication, alcohol and tobacco use except long-acting insulin, 24 hours before the visit. The study participant is not allowed to do strenuous exercise 24 hours prior to the examination. Visit 1 will take approximately two hours. The following questions, measures and samples are obtained:

- Demographic information, medication and medical history are obtained from electronic medical journal and by interview with the study participant
- Weight and height for calculation of body mass index (BMI)
- Office blood pressure and heart rate
- Routine biochemistry
- Test battery A (baseline)
 - Analysis of mitochondrial function of peripheral blood monocytes
 - Sample kept in research biobank for analysis of inflammatory markers
 - Baroreflex sensitivity assessed by continuous ECG and blood pressure

Visit 2 (day 14±6) at Rigshospitalet Glostrup

The study participant will come fasting from the morning and abstinent from medication, alcohol and tobacco use except long-acting insulin, 24 hours before the visit. The study

participant is not allowed to do strenuous exercise 24 hours prior to the examination. Visit 2 will take approximately eight hours. The following measures will be obtained:

- Test battery B (baseline)
 - MRI session with two measurements of: Renal perfusion, renal artery flow, renal oxygen consumption and T_2^* respectively
 - Peripheral blood oxygen saturation by pulse oximetry
 - Blood gas analysis

A standardized morning meal will be given together with the intervention: Institution of 50 mg SGLT2i/placebo. Exactly three hours after intervention, test battery B will be repeated:

- Test battery B (+3 hours)
 - MRI session with two measurements of: Renal perfusion, renal artery flow, renal oxygen consumption and T_2^* respectively
 - Peripheral blood oxygen saturation by pulse oximetry
 - Blood gas analysis

Then a standardized lunch will be given. Exactly six hours after intervention, test battery B will be repeated:

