- Test battery B (+6 hours)
 - MRI session with two measurements of: Renal perfusion, renal artery flow, renal oxygen consumption and T_2^* respectively
 - Peripheral blood oxygen saturation by pulse oximetry
 - Blood gas analysis

Finally, an optional dinner will be offered. See table 1 for a detailed timetable over visit 2.

Table 1

Time	Patients with type 1 diabetes	Healthy Controls
08:00	Kidney MRI (baseline)	Kidney MRI (baseline)
08:30	Blood oxygen saturation (baseline)	Blood oxygen saturation (baseline)
08:40	Arterial blood sample and analysis (baseline)	-
09:00	Intervention: 50 mg SGLT2i/placebo	-
09:00	Standardized morning meal	Standardized morning meal
12:00	Kidney MRI (+3 hours from intervention)	-
12:30	Blood oxygen saturation (+3 hours)	-
12:40	Arterial blood sample and analysis (+3 hours)	-
13:00	Standardized lunch	-
15:00	Kidney MRI (+6 hours from intervention)	-
15:30	Blood oxygen saturation (+6 hours)	-
15:40	Arterial blood sample and analysis (+6 hours)	-
16:00	Optional dinner	-

Timetable over visit 2

Visit 3 (day 28±6) at Steno Diabetes Center Copenhagen

The study participant will be instructed to take 50 mg dapagliflozin / placebo at the time 21:00 on the evening before visit 3. The study participant will come fasting from the morning and abstinent from medication, alcohol and tobacco use except long-acting insulin, 24 hours before the visit. The study participant is not allowed to do strenuous exercise 24 hours prior to the examination. Visit 3 will take approximately one hour. The following measures and samples are obtained:

- Test battery A (baseline)
 - Analysis of mitochondrial function of peripheral blood monocytes
 - Sample kept in research biobank for analysis of inflammatory markers
 - Baroreflex sensitivity assessed by continuous ECG and blood pressure

Visits 4 (day 42±6) and 5 (day 66±6)

Apart from study medication/placebo, study visits 4 and 5 will be identical to visits 2 and 3 but crossed over in terms of SGLT2i/placebo. Table 2 shows study timetable for randomized patients.

Table 2

Visit	Information visit	V1	V2	V3	V4	V5
Site	SDCC	SDCC	RHG	SDCC	RHG	SDCC
Week	0	1	2	4	6	8
Day	0	7	14	28	42	66
Tolerance (\pm days)		± 6				
General						
Informed consent	x					
Assessment of in- and exclusion criteria	x					
If patient: Randomization	x					
Demography		x				
Concomitant medication		x				
Medical history		x				
Weight and height		x				
BP and heart-rate		x				
Routine biochemistry		x				
Endpoints						

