All events meeting the definition of an AE must be collected and reported. This includes events from the first study-related activity after the subject has signed the informed consent until the end of the study. When reporting Adverse Events the following parameters must be recorded: study name, patient identification (subject number, initials, sex, age), event (preferably a diagnosis), IMP, reporter identification (name or initials), causality, outcome. Timelines for reporting of AE's is described in study timetable.

Assessment of adverse event

The following three definitions are used when assessing the severity of an AE: Mild (no or transient symptoms, no interference with the subject's daily activities), Moderate (marked symptoms, moderate interference with the subject's daily activities) and Severe (considerable interference with the subject's daily activities; unacceptable).

The following terms are used when assessing the causality between an AE and the IMP: Probable (good reason and sufficient documentation to assume a causal relationship), Possible (a causal relationship is conceivable and cannot be dismissed) and Unlikely (the event is most likely to ethology other than the IMP (Forxiga®).

Reporting at the end of the study

A final report on the AEs and SAEs is sent to the Danish Medicines Agency, the Regional Scientific Ethics Committee and to AstraZeneca within 12 months after the last patient has completed the project.

Statistical considerations

Sample size

The primary goal is to test the hypothesis that SGLT2 inhibition will improve renal oxygenation with a lowering of medullary T_2^* , as a marker of increased oxygenation. A power calculation was performed, based on data available from the study by Haddock. et al. (15). The mean \pm SD resting medullary T_2^* was 23 ± 4 . Assuming that SGLT2 inhibition will improve oxygenation 20%, the sample size required to demonstrate a significant effect with a power of 80% and a type 1 error of 5%, is 13 subjects per group. To account for technical difficulties, we included 15 in each group. Power calculation was performed using the power statement implemented in the SAS enterprise software 7.1 (SAS Institute, Cary, NC, USA).

Analysis

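### Current or recent SGLT2-inhibitor users with type 1 diabetes are not excluded, and 24 hours off medication is only 1.4 half-lives of dapagliflozin

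*Combined protocol and SAP*

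**What the plan says.** Under Exclusion criteria for all, the only drug-related item is "Treatment with beta-blocking medication". Anticoagulation appears further down, but it bars arterial sampling only, and patients may join without that sampling. No criterion mentions SGLT2 inhibitors.

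Ethical considerations states that "Dapagliflozin is approved for the treatment of type 1 diabetes and type 2 diabetes". The Background section on SGLT2 inhibitors says of dapagliflozin: "The half-life is approximately 17 hours".

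Participants attend Visits 1, 2 and 3 "abstinent from medication, alcohol and tobacco use except long-acting insulin, 24 hours before the visit". Visits 4 and 5 repeat Visits 2 and 3 with the treatment crossed over.

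Table 2 places "Assessment of in- and exclusion criteria" at the information visit, where randomization also takes place. The row "Concomitant medication" is marked at V1 only, after randomization, and no rule says what to do with the answer. Nothing bars non-study SGLT2-inhibitor use between V1 and V5.

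**The concern.** The trial asks what SGLT2 inhibition does acutely to renal oxygenation. That needs baseline and placebo measurements free of SGLT2 inhibition. The Hypothesis section speaks of changes after inhibition is instituted, so new exposure was clearly intended, but no rule enforces it.

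A user who enters could have the pre-dose baselines (V1, V2, V4) and the placebo measurements taken with active drug present. Adjusting for baseline, as the Analysis section plans, does not repair this. A continuing user brings a similar residue to both MRI baselines, so adjustment removes the patient's level but cannot restore a response that is truly smaller. If the T2* response flattens with dose, the dapagliflozin-placebo contrast moves towards zero. The baseline comparison with healthy controls (Assessment of efficacy) could be affected too, because it uses the same pre-dose values.

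Users are plausible in the recruitment pool. The patients have albuminuria and attend a diabetes clinic, and the same section of the protocol describes renoprotective effects of the drug. The information passed on for recruitment covers diagnosis and urine albumin, not medication.

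**Working it through.** **Inputs from the protocol.** Half-life 17 h (Background). Abstinence 24 h (Visits 1 to 3). Scans at 08:00, 12:00 and 15:00 (Table 1), hence 24, 28 and 31 h after a last dose taken at 08:00 the day before. Usual dose 10 mg per day (Patient risks). Study dose 50 mg. Medullary T2* mean 23, SD 4, assumed change 20% (Sample size). Two-sided 5% level (Analysis).

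**1. The plan's own figure.** The Sample size section states that the requirement "is 13 subjects per group. To account for technical difficulties, we included 15 in each group". The difference is 0.20 × 23 = 4.6, and 4.6 / 4 = 1.15 SD. A two-sample t-test with 13 per group has 80.3% power, so the stated figure is reproduced. With 15 per group the power is 86.0%.

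**2. Residue of a last dose.** With first-order elimination, the fraction left is 0.5^(t/17).
- 24 h: 24/17 = 1.41 half-lives, fraction 0.376
- 28 h: 0.319
- 31 h: 0.283

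**3. Daily user at steady state.** Accumulation factor 1/(1 − 0.376) = 1.602. For 10 mg per day:
- baseline: 10 × 0.376 × 1.602 = 6.0 mg, or 12% of 50 mg
- +3 h: 10 × 0.319 × 1.602 = 5.1 mg, or 10%
- +6 h: 10 × 0.283 × 1.602 = 4.5 mg, or 9%

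**4. Contrast lost in one user at +3 h.** The documents give no dose-response for T2*, so this step is an assumption shown as a range. Take E(x) = x/(x + ED50), with ED50 the load giving half the maximal response. The study load is 50 × 0.5^(3/17) = 44.2 mg and the residue is 5.1 mg. The share lost is 1 − [E(44.2 + 5.1) − E(5.1)] / E(44.2).

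| ED50 | Share lost |
|---|---|
| 1 mg | 85% |
| 5 mg | 55% |
| 20 mg | 26% |
| 50 mg | 14% |
| linear response | 0% |

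**5. Effect on the trial.** Attenuation of the mean effect = users × share lost / 15. Power is for 15 per group (two-group test, the protocol's basis) or 15 pairs. The paired columns use SD of the difference = 4 × √(2(1 − r)), with an assumed within-patient correlation r.

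| Users and share lost | Attenuation | Mean effect | Two-group power | Paired, r = 0.5 | Paired, r = 0.3 |
|---|---|---|---|---|---|
| none | 0% | 4.60 | 86.0% | 98.5% | 93.8% |
| one, half | 3.3% | 4.45 | 83.6% | 97.9% | 92.2% |
| one, all | 6.7% | 4.29 | 81.0% | 97.1% | 90.4% |
| two, all | 13.3% | 3.99 | 75.0% | 94.8% | 85.8% |
| three, all | 20.0% | 3.68 | 68.2% | 91.1% | 80.0% |

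At r = 0 the paired power is 83.3% with no users and 78.0% with one user fully lost.

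**The case against.** The strongest reply is that the harm depends on a number the documents do not give. Approval for type 1 diabetes does not show that any eligible patient at this clinic takes the drug, and with no users nothing is lost. That stands: the gap is demonstrated, its consequences are conditional.

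Second, the trial is a cross-over, so two-group power overstates the loss. This also stands. With a within-patient correlation of 0.3 or more, power stays at about 80% or above even with three users fully lost. The protocol gives no correlation, and the attenuation of the estimate itself (3.3% to 13.3% for up to two users) is the same on either basis.

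Third, the range of 14% to 85% rests on an assumed curve. It also uses plasma half-life as a proxy for the renal effect and counts the full 50 mg from time zero, although the Background puts peak concentration at two hours. The 17 h applies to dapagliflozin only. The range is therefore an illustration, and its lower end is zero.

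Fourth, partial safeguards exist. Medication history is taken at V1, before the first study dose, and the protocol describes the exposure as single-dose. Investigators might well turn a user away. But the discretionary criterion concerns patients incapable of taking part, which an SGLT2-inhibitor user is not, and no rule acts on the V1 record.

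Finally, the expected direction is a loss of sensitivity, not a source of false positives. That is true, but a small mechanistic study can also mislead by missing or understating an effect.

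**Conclusion.** The concern holds. As written, the eligibility rules admit a patient who already takes the drug under test, and 24 hours off medication leaves up to 38%, 32% and 28% of the last dose at the three scan times. This part rests only on the protocol's half-life and first-order elimination.

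The consequence for the trial is uncertain. It runs from nothing (no users, or a response linear in dose) to an attenuation of 6.7% of the mean effect for each user whose contrast is wholly lost. On the protocol's own two-group basis, one such user still leaves power above the 80% target and two take it below; a paired analysis is more robust. Confidence in the practical size is moderate at best, because both the number of users and the dose-response are unknown. The change is still worth making: in a 15-patient study the intervention should not be able to enter its own control condition, and preventing it costs very little.

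**What to change.** Add an exclusion for patients with type 1 diabetes: *current or recent treatment with an SGLT2 inhibitor (any dose in the 7 days before the information visit)*. Apply it at the eligibility assessment already scheduled there, before randomization. V1 falls on day 1 at the earliest (day 7 − 6), so at least 8 days separate the last dose from the first study measurement: 0.5^(192/17) = 0.04% of a dapagliflozin dose remains, against 0.1% at 7 days. Seven days exceeds five half-lives (5 × 17 = 85 h, about 3.5 days), which leaves a margin because the protocol gives no half-life for other agents in the class. The clinical team may prefer a longer period.

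Add one sentence: *non-study SGLT2 inhibitors are not allowed until V5*. Extend the concomitant-medication row of Table 2 from V1 to V1–V5 so that this can be checked; this last part is secondary housekeeping. Healthy controls need no new line, since significant endocrine and renal disease already excludes them.

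The cost is one exclusion line, one sentence and four marks in an existing table row. The downside is the loss of a few otherwise eligible patients.
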